# 8.0 STATISTICAL CONSIDERATIONS

This section presents general information about statistical considerations and concepts such as randomization, covariates, statistical power, sample size, and a brief discussion on analysis methodology, as well as some data conventions. Detailed descriptions of the statistical analysis methods and data conventions will be included in a separate document; i.e., the Statistical Analysis Plan (SAP).

# 8.1 Treatment Groups

Group	Description
Group A	Ryanodex ® , as adjuvant treatment to SOC
Group B	SOC only

The following treatment groups will be assessed:

## 8.2 Description of Study Endpoints

### 8.2.1 Efficacy Endpoints

## 8.2.1.1 Primary Efficacy Endpoint

Primary endpoint: Proportion of subjects achieving a total LODS score  $\leq 5$  at or prior to 60 minutes post-randomization.

#### 8.2.1.2 Secondary Efficacy Endpoints:

• Proportion of subjects who achieved a LODS total score  $\leq 5$  at planned timepoints.

•

#### 8.2.2 Safety Assessments

- Adverse events (AEs)
- Vital signs (blood pressure, respiratory rate, and pulse)
- Clinical safety laboratory tests (hematology and coagulation parameters, and blood chemistry)
- Electrocardiogram (ECG)
- Physical examination
- Brief neurological examination
- Oxygen saturation (measured with pulse oximeter)
- End-tidal CO2 (ETCO2)

## 8.3 Sample Size Determination and Rationale

A total of 100 (50 per treatment group) fully eligible (for efficacy) subjects are planned to be randomized in this study. If the study is used for this sample size calculation. The sample size calculation is based on the assumption that for of subjects who receive SOC therapy and Ryanodex® will achieve a LODS score  $\leq 5$  at or prior to 60 minutes post-randomization, compared with only for of subjects who receive SOC therapy alone. Under the above assumption, subjects per treatment group will be required to meet the Type I error rate of 0.05, 2-sided and more than 90% power; for a total of the subjects for the study.

Sample size estimation is depicted in Figure 2.

Figure 2: Sample Size Yielding More than 90% Power for the Study

# 8.4 Randomization

Subjects who meet all inclusion and none of the exclusion criteria will be randomly assigned in a 1:1 ratio to either Group A (Ryanodex® as adjuvant treatment to SOC) or Group B (SOC only) within each study site. The randomization schedule will be generated using an appropriate block size to help maintain treatment groups of equal size.

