- In case a subject was unable to provide consent at the time of enrollment due to the severity of their condition (in accordance with the provisions in 21 CFR 50.24), once the subject is able to understand the nature of the study and the consenting process or the subject's relative becomes available, the subject or relative will be informed that the subject has been enrolled in a clinical study and has been treated on an emergency basis with either standard of care (SOC) or with SOC plus an investigational drug. If the subject or relative refuses consent, the Investigator will stop study assessments and procedures at that time, withdraw the subject from the study, and will not perform any subsequent study assessments.

Study Phases

The study will include the following phases: Screening/Baseline, Treatment Phase, and Discharge.

Planned number of subjects:	An estimated total of 100 subjects will be enrolled in the study (approximately 50 per group).
Diagnosis and main criteria for inclusion:	 Male or non-pregnant female subjects, aged 18 years or older, will be eligible for entry into this study if they are diagnosed with PDIT, as evidenced by all the following at Screening: Core body temperature obtained rectally
	 of >39.5° C (103.1° F). LODS score ≥ 6. In the event of any delay in obtaining the lab results for baseline LODS score determination, subject may be enrolled and randomized if all the other eligibility criteria are met; after enrollment if the pending baseline LODS score turns out to be < 6, subject will be withdrawn from the study and

	subsequently replaced with a new subject
	 Known or suspected recent use of a psychostimulant drug, in the judgement of the investigator.
	• Negative pregnancy test for female subjects. If positive, female subjects must be excluded from participating in the study. In the event of any delay in obtaining pregnancy result, subject may be enrolled and randomized if all other eligibility criteria are met. However, female subjects randomized to Treatment Group A (Ryanodex as adjuvant treatment to SOC) must not be dosed with Ryanodex until a negative result of the pregnancy test is available. If a positive pregnancy test is noted after randomization, subject will be withdrawn from the study and subsequently replaced with a new subject to complete the ITT population.

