Main criteria for exclusion:	A subject diagnosed with PDIT will be excluded from entering the study if he or she presents with or, in the judgment of the Investigator, meets any of the following criteria at Screening:
	• Diagnosed with or is suspected to have an acute clinically severe infection, which in the opinion of the Investigator may increase the subject's risk for participating in the study and/or may impair the ability of performing and/or interpreting study assessments.
	• Severe hyperthermia secondary to a condition other than PDIT (e.g., thyrotoxicosis, pheochromocytoma, or brain hemorrhage).
	• Likelihood of head trauma in the past 3 months, or other systemic disease that might increase the subject's risk for participating in the study and/or may impair the ability of performing and/or interpreting study assessments.
	• Positive pregnancy test or evidence of active lactation.
	 Known history of allergy or hypersensitivity to dantrolene.
	 Known history of seizure disorders or epilepsy.

	• Current or prior use (within the past 2
Test product, dose, and mode of administration:	Ryanodex [®] : dantrolene sodium for injectable suspension; 250 mg/vial to be reconstituted in 5 mL of sterile water for injection (without a bacteriostatic agent) to yield a 50 mg/mL suspension; to be administered as a rapid IV push of 2.5 mg/kg.
Reference therapy, dose, and mode of administration:	 Standard of Care (SOC): all subjects in both treatment groups will receive SOC. Supportive Measures: all subjects should receive adequate supportive measures for treating PDIT, as well as medically acceptable treatment for complications and comorbidities.

Endpoints:

Primary Efficacy Endpoint:

The primary efficacy endpoint for this study is proportion of subjects achieved a total LODS score \leq 5 at or prior to 60 minutes post-randomization.

Secondary Efficacy Endpoints:

• Proportion of subjects who achieved a LODS total score ≤ 5 at planned time points.

Dantrolene plasma concentration:

Plasma sample data will be presented for all subjects with informed consent and/or summarized.

Safety Assessments:

- Adverse events (AEs)
- Vital signs (blood pressure, respiratory rate, and pulse)
- Clinical safety laboratory tests (hematology and coagulation parameters, and blood chemistry)
- Electrocardiogram (ECG)

- Physical examination
- Brief neurological examination
- Oxygen saturation (measured with pulse oximeter)
- End-tidal CO₂ (ETCO₂)

Sample size:

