# 8.5 Blinding

This is an open-label study; no blinding of study drug will be performed.

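### Open-label randomisation blocked within site does not commit to varied, undisclosed block sizes, so some allocations could be known in advance while part of entry is judged

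*SAP*

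**What the plan says.** - **Allocation.** SAP section 8.4 has subjects "randomly assigned in a 1:1 ratio to either Group A" or "Group B (SOC only) within each study site". On blocking it says only: "The randomization schedule will be generated using an appropriate block size to help maintain treatment groups of equal size". It gives no number. It does not say whether the size varies, whether sites are told it, or how the next assignment is concealed.
- **Blinding.** SAP section 8.5: "This is an open-label study; no blinding of study drug will be performed". Staff at a site can therefore see every earlier assignment made there.
- **Measured entry criteria.** The Protocol synopsis (section 1.0) requires a rectal temperature above 39.5 °C and a LODS score of at least 6.
- **Pending results.** The LODS criterion carries an exception: "LODS score ≥ 6. In the event of any delay in obtaining the lab results for baseline LODS score determination, subject may be enrolled". A subject later found below 6 is withdrawn and replaced. A similar exception covers a delayed pregnancy test.
- **Judged entry criteria.** Drug exposure is "Known or suspected recent use of a psychostimulant drug, in the judgement of the investigator". A subject is excluded who, in the investigator's judgement, "meets any of the following criteria at Screening". Those criteria include suspected severe infection, likely recent head trauma and other systemic disease that might raise risk.
- **Primary analysis set.** The synopsis limits ITT to randomised subjects whose psychostimulant exposure was confirmed in blood.

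**The concern.** Blocking within site, visible assignments and partly judged eligibility are the conditions under which staff can count back through a block and foresee the next arm. An expectation about the next arm can then affect whether a borderline patient is judged eligible, or whether to randomise while a result is pending.

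If patients entered on an expected Ryanodex slot differ in prognosis from those entered on an expected SOC slot, the comparison of LODS response at 60 minutes is biased and its false-positive rate rises above 5%. SAP section 8.9 adjusts for baseline values, but adjustment reaches only what is recorded, and steering of this kind would rest on bedside impressions. Varying and withholding the block sizes is a well-established, nearly free safeguard that the wording does not promise.

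**Working it through.** **Inputs.** From the documents: 1:1 allocation within site, open label, 50 per group, two-sided 5% level. Assumed, because not given: block sizes, 5 or 10 subjects per site, 40% response in both arms, and the amount of steering.

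**The plan's own figures.** There is no block size or predictability figure to reproduce. The response rates behind the 100 subjects are withheld, so that number cannot be reproduced either. For scale, 50 per arm gives about 90% power for differences of roughly 27 to 32 points (10% vs 37%: 0.902; 40% vs 72%: 0.909).

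**1. One known block size, complete blocks.** For block size b = 2m, the share of allocations that are certain is 1/(m+1). Best-guess accuracy is 1/2 + (2^b/C(b,m) − 1)/(2b).
- b = 4: certain 1/3 = 33.3%; guess 0.5 + (16/6 − 1)/8 = 70.8%.
- b = 6: certain 1/4 = 25.0%; guess 68.3%.
- b = 8: certain 1/5 = 20.0%; guess 0.5 + (256/70 − 1)/16 = 66.6%.

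**2. Allowing for unfinished blocks.**
- 10 per site, b = 4: two complete blocks give 8 × 1/3 = 2.67 certain slots, and the last two are never forced, so 2.67/10 = 26.7%.
- 10 per site, b = 8: 8 × 1/5 = 1.6, so 16%.
- 5 per site, b = 4: (4 × 1/3)/5 = 26.7%.
- 5 per site, b = 6: slot 4 is forced with probability 0.1 and slot 5 with probability 0.4, so 0.5/5 = 10%.
- 5 per site, b = 8: slot 5 is forced with probability 2/70, so 0.6%.

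**3. Varied sizes.** Here the observer knows the set of sizes but not their order, and updates by Bayes' rule after each assignment (10 subjects per site).

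| Schedule | Certain | Best guess correct |
|---|---|---|
| Fixed 4, known | 26.7% | 68.3% |
| Fixed 8, known | 16.0% | 64.0% |
| 4, 6 | about 6% | about 68% |
| 2, 4, 6 | 3.2% | 69.0% |
| 4, 6, 8 | 2.4% | 65.9% |

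**4. Illustrative type I error.** Suppose the response chance of those enrolled is δ higher when Ryanodex is predicted and δ lower when SOC is predicted. If only certain slots (share c) are steered, the spurious difference is s = 2δc. If every best guess (accuracy g) is acted on, s = 2δ(2g − 1). SE = √(2 × 0.4 × 0.6/50) = 0.098, and type I error = Φ(−1.96 + s/SE) + Φ(−1.96 − s/SE).

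| Steering | Fixed 4, known | 4, 6, 8 varied |
|---|---|---|
| Certain slots, δ = 0.10 | s = 0.053; 8.5% | s = 0.005; 5.0% |
| Certain slots, δ = 0.20 | s = 0.107; 19% | s = 0.010; 5.1% |
| Every guess, δ = 0.10 | s = 0.073; 11.6% | s = 0.064; 9.9% |

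Without steering the rate is 5%. Varying the sizes removes almost all certainty but little of the guessing advantage.

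**The case against.** A reader might infer from section 8.4 that the trial used one fixed block size known to sites, so that allocations were often predictable. The documents do not support that. The singular may be ordinary drafting for a size to be chosen later, and leaving the number out is consistent with keeping it from sites.

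Nor does silence on concealment show there was none. The public file holds the synopsis and part of section 8, section 8.6 has no visible text, and section 8.0 calls itself general information. A randomisation procedure may stand elsewhere.

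It would also be too strong to say that entry rests on judgement:
- Temperature and LODS are measured thresholds, and a pending LODS found below 6 leads to withdrawal and replacement.
- Blood confirmation means that enrolling a merely suspected user adds nobody to the ITT set if the test is negative.
- Waiting for a result leaves the next slot unchanged unless another patient is randomised at that site meanwhile.
- Section 8.11.1 reports the disposition of all screened subjects, which could leave a trace of selective exclusion.

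Finally, the error rates above require steering to occur. δ = 0.20 means a 40-point prognostic gap, larger than the 27 to 32 points the trial is sized to detect.

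All of this stands, and it limits the size of the point. It does not remove it. Choice among true users and the judged exclusions remain open, LODS may be unknown when the decision is made, and the wording permits a small fixed block.

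**Conclusion.** The point holds in a limited form. Section 8.4 allows a single block size within site in an open-label trial with partly judged entry, and does not commit to the simple safeguard against it. If the block is 4 and its size is known or inferred, about a quarter of allocations could be foreseen at sites of 5 or 10 subjects. Larger blocks give fewer, down to 0.6% for blocks of 8 at sites of 5, where guesses are still right 58% of the time.

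The share foreseen depends on the block size, on sites learning it, and on subjects per site, none of which the documents give. The type I error figures are illustrations under assumed steering. They are not estimates for this trial, and nothing in the documents shows that steering occurred.

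**What to change.** Reword section 8.4 along these lines:

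> *Within each site, permuted blocks of randomly varying size (avoiding blocks of 2) will be used. Block sizes are held by the randomisation provider and not disclosed to sites. The allocation is released only after eligibility has been recorded, with any pending result marked as such.*

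Three sizes are better than two: 4 and 6 alone leave about 6% of allocations certain, against 2.4% for 4, 6 and 8. If such a procedure already exists in another document, a cross-reference is enough.

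Recording eligibility first does not stop guessing. It prevents eligibility being revised once the arm is known, and makes discretionary decisions auditable. Because guess accuracy stays near 66%, the sponsor could also consider whether blocking within very small sites is needed.

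**Cost.** A schedule setting, a few sentences, and a brief eligibility confirmation before release, which is a real if small step in an emergency setting. Possible imbalance within a site grows slightly: at most half the block, so 4 for a block of 8 against 2 for a block of 4.

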# 8.5 Blinding

This is an open-label study; no blinding of study drug will be performed.

# 8.6

# 8.7 General Statistical Considerations

Baseline body temperature will be the first rectal temperature  $>39.5^{\circ}$  C taken during the Screening Phase. Baseline results for other study assessments will be the value closest in time to the baseline rectal temperature and prior to randomization. The SAP may specify additional data handling rules.

All collected study data will be presented in subject data listings. Statistical analyses will be performed using SAS® for Windows, version 9.4 or later. Descriptive statistics (n, mean, standard deviation, median, minimum and maximum) will be presented by treatment group for continuous variables. Frequencies and percentages will be presented by treatment group for categorical variables.

## 8.7.1 Data to Be Analyzed

will analyze the study data. Data handling will be the responsibility of **1**. The data will be inspected for inconsistencies by performing validation checks.

All data collected during the study will be reported. All details regarding the statistical analysis and the preparation of tables, listings, and figures will be described in the SAP prepared by and approved by the Sponsor before database lock. The statistical analysis will be

performed by

## 8.8 Analysis Populations

#### 8.8.1 Intent-to-Treat (ITT) population

The Intent-to-Treat (ITT) population is defined as

#### 8.8.2 Modified Intent-to-Treat (MITT) population

The Modified Intent-to-Treat (MITT) population is

The MITT analysis of primary and secondary endpoints will be considered supportive.

#### 8.8.3 Per Protocol (PP) Population

The Per Protocol (PP) population is defined

· / · ·			
		•	

#### 8.8.4 Safety Population

The Safety population is defined as any subject who received any study treatment (SOC only or SOC with Ryanodex®). This population will be used for the analysis of safety parameters.

## 8.9 Covariates

For efficacy analyses, the baseline values will be used as covariates in the analysis models.

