#### Primary Endpoint:

will be used to compare the proportion of subjects achieved a total LODS score  $\leq$  5 at or prior to 60 minutes post-randomization.

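### Allocation is blocked within site, but section 8.9 names only baseline values as covariates; an efficacy analysis that ignores site would be mildly conservative if sites differ in response

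*SAP*

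**What the plan says.** - **Allocation (SAP 8.4).** Subjects are "randomly assigned in a 1:1 ratio to either Group A" (Ryanodex plus SOC) "or Group B (SOC only) within each study site". Blocking is used: "The randomization schedule will be generated using an appropriate block size to help maintain treatment groups of equal size". The block size and the number of sites are not given. The protocol synopsis (Methodology) describes a multiple-site trial in pre-hospital emergency units.
- **Covariates (SAP 8.9).** The whole section is one sentence: "For efficacy analyses, the baseline values will be used as covariates in the analysis models". It does not say which baseline values are meant, and it does not mention site.
- **Primary comparison (SAP 8.11.4.1, Primary Endpoint).** The method's name is removed. The readable text starts at "will be used to compare the proportion of subjects achieved a total LODS score".
- **Secondary endpoints (SAP 8.11.4).** A Cox model is named for time-to-event data, with no site stratum in the readable text.
- **Deferral (SAP 8.0 and 8.11).** Detailed methods are left to a separate SAP, to be approved before database lock. That document is not among those available.

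**The concern.** Blocking within site forces near-equal arms at each site, which takes between-site variation out of the treatment contrast. An analysis that ignores site still counts that variation in its standard error. The p-value is then too large, the interval too wide, and part of the precision bought by the design is not used.

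Site differences are plausible here. The protocol's account of mass-gathering medicine stresses weather, crowding and access problems that vary from event to event, and supportive care is left to investigator judgement. The number of sites and the size of any between-site difference are not stated.

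Timing also matters. The trial is open-label (SAP 8.5). If stratification, pooling of small sites and the choice of baseline covariates are settled only shortly before database lock, they could be settled by people who have seen outcomes by arm.

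**Working it through.** **Inputs from the documents.** 100 subjects, 50 per group; 1:1 blocked allocation within site; two-sided 0.05; more than 90% power (SAP 8.3, 8.4).

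**Assumed, because not stated or not readable.** Response rates, number of sites, block size (4), and between-site SD on the logit scale.

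**Step 1: the plan's own figure.** The sample size statement is "A total of 100 (50 per treatment group) fully eligible (for efficacy) subjects are planned to be randomized in this study", and the required number "will be required to meet the Type I error rate of 0.05, 2-sided and more than 90% power". Both response rates are redacted, so 50 per group cannot be reproduced. It can be inverted. With the pooled-variance formula and no continuity correction, 50 per group gives 90% power for control/treatment rates of about 0.10/0.37, 0.20/0.50, 0.30/0.62, 0.40/0.72, 0.50/0.80 or 0.60/0.88. Check for 0.30 v 0.62, mean rate 0.46:

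- z = [0.32 × √50 − 1.96 × √(2 × 0.46 × 0.54)] / √(0.30 × 0.70 + 0.62 × 0.38) = (2.263 − 1.381) / 0.668 = 1.32, so power is 0.907.

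This pair is therefore a fair stand-in for the redacted assumption.

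**Step 2: large-sample size of the effect.** Let ρ be the share of the response variance p(1−p) that lies between sites. With balance inside every site, the null variance of the unstratified z statistic is 1 − ρ rather than 1, so

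- actual α = 2 × [1 − Φ(1.96 / √(1 − ρ))].

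For p = 0.30:

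| Site SD | Site rates at ±1 SD | ρ | 1.96/√(1−ρ) | Actual α |
|---|---|---|---|---|
| 0.5 | 0.20-0.40 | 0.048 | 2.01 | 0.0445 |
| 1.0 | 0.12-0.50 | 0.157 | 2.13 | 0.0328 |
| 1.5 | 0.06-0.58 | 0.274 | 2.30 | 0.0214 |

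**Step 3: simulation at the planned size.** 20,000 trials per setting, equal sites, blocks of 4, marginal rates held fixed. An unstratified pooled chi-square test is compared with Cochran-Mantel-Haenszel (CMH) stratified by site. The Monte Carlo standard error is √(0.05 × 0.95 / 20,000) = 0.0015 for a type I error and √(0.92 × 0.08 / 20,000) = 0.0019 for a power.

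| Site SD | Sites | Type I, unstratified | Type I, CMH | Power 0.30 v 0.62, unstratified | Power, CMH | CMH minus unstratified (points) |
|---|---|---|---|---|---|---|
| 0 | 5 | 0.051 | 0.051 | 0.913 | 0.912 | −0.1 |
| 0 | 10 | 0.055 | 0.053 | 0.915 | 0.903 | −1.2 |
| 0 | 20 | 0.052 | 0.050 | 0.910 | 0.889 | −2.1 |
| 0.5 | 5 | 0.044 | 0.048 | 0.919 | 0.922 | +0.3 |
| 0.5 | 10 | 0.047 | 0.049 | 0.916 | 0.913 | −0.3 |
| 0.5 | 20 | 0.048 | 0.049 | 0.915 | 0.904 | −1.1 |
| 1.0 | 5 | 0.036 | 0.049 | 0.926 | 0.944 | +1.8 |
| 1.0 | 10 | 0.036 | 0.047 | 0.924 | 0.942 | +1.8 |
| 1.0 | 20 | 0.038 | 0.049 | 0.926 | 0.938 | +1.2 |
| 1.5 | 5 | 0.028 | 0.050 | 0.925 | 0.963 | +3.8 |
| 1.5 | 10 | 0.027 | 0.046 | 0.932 | 0.966 | +3.4 |
| 1.5 | 20 | 0.027 | 0.046 | 0.932 | 0.963 | +3.1 |

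Rates of 0.40 v 0.72 and 0.20 v 0.51 give the same pattern. The loss in step 3 is smaller than the formula in step 2 suggests. One reason is that a handful of sites shows, on average, less between-site variance than the population they come from.

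**Step 4: uneven sites and pooling.** A separate simulation gave unstratified type I error of 0.033-0.043 at SD 1 and 0.030-0.034 at SD 1.5, with power 1-2 and 3-4 points below CMH. With no site effect, unpooled CMH lost up to about 3 points across 20 uneven sites. With small sites pooled the loss was about 1 point.

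**The case against.** The strongest reply is that the documents do not show that the primary test ignores site. Its name is redacted, a site-stratified CMH test would fit the gap, and blacked-out text is not an omission. A CMH stratum is also not a model covariate, so a covariates section need not list it. Section 8.9 does not say that baseline values are the only adjustment, and the detail is deferred to a separate SAP. This stands. A reader might infer that the primary test is unstratified, but the text does not support that. What remains is that 8.4 makes site a stratum while the readable adjustment rule for all efficacy models, and the readable Cox model, do not mention it.

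A second reply is that the size rests on assumptions. Baseline covariates could absorb part of the site effect, which was not modelled, and common eligibility thresholds and a defined SOC limit the spread between sites. This also stands, and it is why the result is given as a range.

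A reader might also infer that site variation pulls power well below 90%. Such a picture appears if the within-site odds ratio is held fixed. With control response about 35%, odds ratio 3.9 and SD 1.4, power is 73-74% unstratified and 79-81% stratified. Most of that fall arises because a fixed within-site odds ratio implies a smaller marginal difference as sites spread apart, and the stratified test falls too. With marginal rates fixed, the unstratified test kept 0.906-0.941 in every simulated setting with those fixed rates.

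**Conclusion.** The point holds as a conditional matter of specification and efficiency. If an efficacy analysis ignores site and sites differ in response, the nominal 0.05 test runs at about 0.03-0.04. It gives up about 1-2 points of power at site SD 1 and 3-4 points at SD 1.5 against a site-stratified test. At SD 0.5 nothing of practical importance changes.

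The error is in the conservative direction: type I error is not inflated and the stated power is not shown to fail.

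The sizes rest on assumed rates near 30% v 62%, 5 to 20 sites, a comparison of proportions without baseline covariates, and all 100 subjects analysed as allocated. Withdrawals with replacement, and the blood-test condition for the ITT population (protocol synopsis), could disturb balance within sites and were not modelled. Nor was the Cox model.

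**What to change.** In SAP 8.9 and 8.11.4.1, unless the redacted method already does this:

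1. Stratify the primary comparison by randomisation site, for example with CMH, and state a rule for pooling small sites that is fixed before outcomes are reviewed.
2. Report a site-stratified risk difference with its confidence interval.
3. Say which baseline values are covariates, and include pooled site as a stratum in the models that use them, including the Cox model.

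If the redacted test is already stratified by site, a sentence in 8.9 bringing the covariate models into line is enough.

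The cost is wording and a pooling rule. If sites do not differ, power falls by about 1 point with pooling, or by up to 2-3 points without pooling when there are many very small sites. The pooling rule is therefore a necessary part of the change.
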